1.4.2 Specific research objectives (corresponding to six sub-studies)

Sub-study 1: A logistic regression modelling study to determine whether baseline grip strength and sedentary time predict BMD response ($\geq 1\%$ improvement) to RT, thereby identifying “responders” for individualised exercise prescription.

Sub-study 2: A dose–response study using generalised additive models (GAM) to analyse the minimum effective frequency of RT and to explore nonlinear relationships between training frequency and BMD/balance function (Berg Balance Scale), identifying threshold effects.

Sub-study 3: A mediation analysis examining whether change in grip strength (Δ HGS) mediates the effect of RT on BMD, providing empirical evidence for the muscle–bone coupling mechanism.

Sub-study 4: An empirical analysis investigating whether prior experience with digital devices and technology acceptance scores are associated with higher training adherence, informing the optimisation of smart elderly care platform design.

Sub-study 5: A clustering and visualisation study of QoL trajectories (SF-36) to identify patterns of change in physical (PCS) and mental (MCS) health dimensions, enabling subgroup-targeted intervention strategies.

Sub-study 6: A micro-level cost-effectiveness analysis calculating the marginal cost per 1% BMD improvement based on actual financial data, constructing a community RT cost-effectiveness evaluation model to support policy and health-insurance alignment.

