1.4.5 Application innovations

Community RT responder screening tool: A nomogram based on baseline grip strength, sedentary time, and BMI for rapid identification of high-responder populations (BMD improvement $\geq 3\%$; AUC = 0.82), guiding targeted resource allocation [Sub-study 1].

Low-technology smart supervision protocol: A “dual-track supervision model”—digital track (WeChat-based training reminders and video guidance) and manual track (weekly telephone follow-up and periodic home visits by community workers).

Health insurance alignment decision tree: Cost-effectiveness outputs translated into policy pathways based on the ICER-to-GDP ratio: when ICER does not exceed one times per-capita GDP, the intervention enters the basic public health service package; when it exceeds this threshold, supplementary commercial health insurance is required.

Chapter 2 Literature Review and Theoretical Foundations

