3.2 Primary Research Hypotheses (H1–H6)

3.2.1 H1 (Sub-study 1)

Among older adults with primary OP receiving the smart RT intervention, baseline health status and health literacy differentially influence RT response. Specifically, participants with lower baseline BMD but higher eHLQ/technology acceptance scores are more likely to achieve clinically significant BMD improvement ($\geq 3\%$ lumbar spine increase). The rationale is twofold: lower baseline BMD provides greater room for improvement, and higher health literacy and technology acceptance enable more complete understanding and execution of the training protocol.

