4.4 Primary and Secondary Outcome Measures

4.4.1 Primary outcomes (T2)

BMD: Lumbar spine BMD (g/cm^2) measured by DXA (e.g., GE Lunar Prodigy), reported as absolute values and percentage change from baseline. Within-day coefficient of variation for lumbar spine BMD is approximately 1%.

Physical function: SPPB total score (0–12), comprising standing balance, 4-metre gait speed, and five-times chair-stand subtests (each scored 0–4).

Quality of life: SF-36 Physical Component Summary (PCS) and Mental Component Summary (MCS), each scored 0–100.

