4.7 Ethical Approval

4.7.1 Ethics committee and approval status

Ethical approval is pending.

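### Sub-study 1 fixes its responder outcome two ways (≥1% and ≥3%), names three predictor sets, frames H1 in trained participants only, and quotes an unsourced AUC for a model not yet built

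*Protocol*

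**What the plan says.** Three places in the Protocol define what Sub-study 1 predicts and from what.

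- **Section 1.4.2 (objective).** A logistic model is to test whether "grip strength and sedentary time predict BMD response ($\geq 1\%$ improvement) to RT". The skeletal site is not named.
- **Section 3.2.1 (H1, Sub-study 1).** Participants with lower baseline BMD and higher eHLQ or technology acceptance scores are expected to "achieve clinically significant BMD improvement ($\geq 3\%$ lumbar spine increase"). The population is given as "Among older adults with primary OP receiving the smart RT intervention".
- **Section 1.4.5 (application, tagged Sub-study 1).** A nomogram on grip strength, sedentary time and BMI is to find "high-responder populations (BMD improvement $\geq 3\%$; AUC = 0.82") and to guide where resources go.

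On measurement, section 4.4.1 states: "Within-day coefficient of variation for lumbar spine BMD is approximately 1" per cent. Section 4.4.3 requires one DXA device with daily phantom calibration and prefers, but does not require, the same technician over time. Section 1.4.1 expects a lumbar spine gain of at least 3% at 8 months and ties that figure to a clinical significance threshold. Section 4.7.1 states: "Ethical approval is pending".

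**The concern.** A responder model is defined by its outcome, its predictors and its population. The Protocol gives two outcomes and three predictor sets, and never says which ones the logistic model uses. If both cut-offs stay open, the choice can be made after the data are seen.

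The lower cut-off is the same size as the error of a single scan, so part of what it labels as response could be measurement error. How large a part depends on how much true change there is.

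H1 is posed among trained participants. Without the control arm, a predictor of response to training looks the same as a predictor of natural drift, of scan error or of regression to the mean. H1's own leading predictor, low baseline BMD, is the most exposed. Error that lowers a baseline scan also raises the apparent gain, so low baseline would appear to predict response even if training did nothing.

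The AUC of 0.82 is written as a property of a tool that the trial has yet to develop. The output is meant to steer individual prescription and the allocation of community resources, so an unsupported performance figure matters.

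**Working it through.** The Protocol states no misclassification rate, so there is no figure of its own to reproduce.

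**1. Passages side by side**

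| Place | Cut-off | Site | Predictors |
|---|---|---|---|
| 1.4.2 | ≥1% | not named | grip strength, sedentary time |
| 1.4.5 | ≥3% | not named | grip strength, sedentary time, BMI |
| 3.2.1 (H1) | ≥3% | lumbar spine | baseline BMD, eHLQ/technology acceptance |

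**2. Measurement error in a two-scan change**

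Input: CV about 1% (section 4.4.1). Assumptions: one scan per visit, independent normal errors.

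- SD of percentage change = √2 × 1% = 1.414%.
- 95% least significant change = 1.96 × 1.414% = 2.77%.

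**3. Share passing each cut-off if true change is exactly zero:** 1 − Φ(cut-off / (√2 × CV)).

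The stated CV is within-day. Precision over 8 months may differ, so the other rows are assumed values.

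| CV | 95% least significant change | pass ≥1% | pass ≥3% |
|---|---|---|---|
| 0.8% | 2.22% | 18.8% | 0.4% |
| **1.0% (stated)** | **2.77%** | **24.0%** | **1.7%** |
| 1.2% | 3.33% | 27.8% | 3.9% |
| 1.5% | 4.16% | 31.9% | 7.9% |
| 2.0% | 5.54% | 36.2% | 14.4% |

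A simulation of the ratio of two noisy scans at CV 1% gave 24.0% and 1.8%. If the true change is a loss rather than zero, fewer pass ≥1%: 14% at an assumed −0.5% and 8% at −1%.

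**4. What happens if training works**

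Assume true change is normal with between-person SD 2% (not in the Protocol) and CV 1%. The SD of observed change is √(2² + 1.414²) = 2.45%. *Misclassified* means that observed and true change fall on opposite sides of the cut-off.

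| Mean true gain | pass ≥1% | pass ≥3% | misclassified at ≥1% | misclassified at ≥3% |
|---|---|---|---|---|
| 0% | 34% | 11% | 17.8% | 8.3% |
| 2% | 66% | 34% | 17.8% | 17.8% |
| 3% (expected, section 1.4.1) | 79% | 50% | 13.4% | 19.6% |

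Among those passing ≥1%, the share with no true gain is about 11% when the mean gain is zero and about 1% when it is 3%. Error is greatest where the cut-off sits at the centre of the distribution. At the expected gain, that is the 3% cut-off.

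**The case against.** Four objections carry weight.

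- **The 24% describes the wrong people.** It holds only for a true change of exactly zero. H1 concerns trained participants, for whom the Protocol expects a 3% mean gain. A reader might infer that a ≥1% model would be trained largely on noise. Under the Protocol's own expectation it would not, because only about 1% of those passing would have no true gain (SD 2% assumed). This objection stands.
- **The least significant change does not settle the matter for ≥3%.** A reader might infer that 3% is right because it exceeds 2.77%. That margin disappears at an assumed longitudinal CV of 1.2%, where the limit is 3.33%. The limit is also a criterion for judging one person's change. In a regression, outcome error mainly weakens discrimination. This stands too, so the case for ≥3% has to rest on consistency.
- **The single-arm reading is partly inferred.** Section 1.4.2 names no arm, section 3.3.1 lists allocation as the primary independent variable, and section 3.3.3 commits to controlling for osteoporosis medication. A reader might infer that the control arm goes unused and that drug effects are ignored. The documents do not establish the first and speak against the second. H1's population is nevertheless explicit, and covariate adjustment within one arm does not remove drift or regression to the mean.
- **Some detail belongs in an analysis plan.** Section 4.1.2 commits Sub-study 1 to TRIPOD, and validation methods can be left to the plan. But the cut-offs, predictor sets and AUC are stated in the Protocol and either conflict or lack support. That is different from missing detail.

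The word high-responder in section 1.4.5 could suggest a second tier. No tier is defined, and H1 does not use the term.

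**Conclusion.** The concern holds as an internal contradiction. Sub-study 1 has two cut-offs, three predictor sets, and an AUC of 0.82 given without a source for a model still to be built. Pending ethics approval fits with no trial data existing yet, but that is an inference. The defect is that the figure has no stated basis.

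The noise argument holds conditionally. With zero true change and the within-day CV carried over 8 months, 24% pass ≥1% and 1.7% pass ≥3%; at an assumed CV of 1.5% the shares are 32% and 8%. With the expected 3% gain and an assumed SD of 2%, misclassification is 13.4% at ≥1% and 19.6% at ≥3%. Which cut-off is noisier therefore depends on an effect not yet known.

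As framed, H1 cannot separate predictors of response to training from predictors of drift, measurement error or regression to the mean.

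The trial's main comparison is untouched: section 4.4.1 reports lumbar BMD as absolute value and percentage change, with no responder cut-off. This should be fixed, but it does not threaten the primary result.

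**What to change.** 1. Make the main Sub-study 1 analysis a regression of continuous T2 lumbar spine BMD, adjusted for baseline, in both arms, with predictor × arm interactions. Use one predictor list in sections 1.4.2, 1.4.5 and 3.2.1. State that the interactions will be imprecise in a small sample.
2. If a binary label is kept for the nomogram, use one lumbar spine cut-off throughout. ≥3% agrees with H1, the nomogram and the benchmark in section 1.4.1. Remove ≥1%, or define it explicitly as a separate tier.
3. Delete the AUC of 0.82 or label it as a target. Report the AUC from the trial's own data, corrected for optimism.

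The cost is Protocol wording and a different regression on data already planned in both arms. The stated AUC is lost as a headline figure. Settling this before outcome data are seen keeps the choice of cut-off prespecified.

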1.4 Research Objectives and Innovations

1.4.1 Overall research objective

The overarching objective is to validate the comprehensive benefits of “community-based

smart RT” for BMD, muscular function, and quality of life (QoL) among older adults with OP, and to establish a sustainable implementation pathway. Specifically: (a) quantify the effect of 8-month RT on lumbar spine BMD through an RCT, with an expected increase of $\geq 3\%$ (benchmarked against the IOF clinical significance threshold); (b) design a long-term intervention strategy with 8 months of supervised training (twice weekly) followed by 12 months of low-frequency maintenance (once monthly); and (c) develop an integrated smart elderly care system featuring real-time wearable monitoring, AI-driven exercise prescription adjustment, and community-station offline supervision, achieving “data–professional–family” three-tier coordination.

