1.4.4 Methodological innovations

Small-sample dose–response GAM optimisation: Employs penalised smoothing splines ($k = 3$) to constrain degrees of freedom, stably identifying threshold effects of training frequency on BMD improvement under $n < 100$ conditions, resolving the overfitting problem of conventional regression [Sub-study 2].

Mixed longitudinal trajectory analysis (MLTA): Integrates latent class growth modelling (LCGM) with mixed-effects models to identify QoL change subgroups (e.g., “rapid responders” vs. “slow improvers”) from SF-36 data, enhancing small-sample trajectory classification validity [Sub-study 5].

RCT-embedded micro-costing: Constructs a dynamic “BMD gain–cost” model in a community equipment-sharing scenario, incorporating equipment-sharing cost reduction, long-term fracture-prevention benefits, opportunity costs, and personnel/time costs. Calculates ICER for BMD; Markov modelling projects multi-year cost–utility [Sub-study 6].

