3.2.2 H2 (Sub-study 2)

A nonlinear relationship exists between actual RT dose and outcomes, potentially exhibiting a J- or U-shaped curve. Adherence is operationalised as the proportion of planned sessions completed and mean training-intensity attainment; dose is quantified as cumulative resistance-training volume. We expect that as dose increases from low to moderate, outcomes (e.g., BMD change) improve substantially, but beyond a certain high dose, marginal benefits plateau or decline, indicating an optimal dose range.

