4.1 Study Design Overview

4.1.1 Primary study design

This study employs a two-arm, parallel-group, assessor-blinded randomised controlled trial (RCT), with 1:1 allocation to the intervention and control groups. Outcome assessors are blinded to group assignment to minimise measurement bias. The protocol and reporting adhere to the CONSORT 2010 Statement, including transparent documentation of randomisation sequence generation, allocation concealment, blinding, and participant flow.

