The intervention follows the FITT-VP exercise prescription principles. Frequency: 3 sessions/week. Time: 5-minute warm-up, 30–50 minutes of RT (including 2–3 minutes inter-set rest), 5-minute cool-down stretching. Type: moderate-intensity whole-body resistance exercises targeting weight-bearing muscle groups. Intensity: initial 50–60% 1RM (RPE 3–4),

progressing to 70–80% 1RM (RPE 5–6). Volume: weeks 1–4, one set per exercise (10–15 repetitions); weeks 5–12, two sets per exercise. Equipment: colour-coded elastic resistance bands (yellow 10 lb/4.5 kg; pink 15 lb/6.75 kg; blue 20 lb/9.07 kg; purple 30 lb/13.6 kg), assigned based on baseline functional assessment.

Table 4.3.1 (2), Specific resistance exercise movements 具体抗阻运动动作

Action name (muscle group exercised)		Key Points
Lower back exercise 腰背部运动		
1	Back stretch (Sacrospinal muscles)	Lie prone, place a pillow under your abdomen, put your arms at your sides, use your back strength to lift your upper body, hold for 3 to 5 seconds, then slowly lower it. Rest for 2 to 3 minutes between sets
Lower limb exercise 下肢运动		
2	Band prone position Knee flexion (hamstrings, etc.)	Lie prone, fix the ankle joint with an elastic band, fix the left leg, bend the right knee as much as possible, hold for 3 to 5 seconds, then slowly lower it. Alternate between left and right for 1 to 2 sets. Rest for 2 to 3 minutes between sets
3	Elastic band supine straight leg raise (quadriceps, etc.)	Supine position, fix the ankle joint with an elastic band, fix the left leg, dorsiflex the ankle joint of the right leg, straighten and lift until you can't go any further, hold for 3 to 5 seconds and then slowly lower, fix the pelvis and lumbar spine with both hands. Alternate between left and right for 1 to 2 sets each. Rest for 2 to 3 minutes between sets
4	Elastic band sitting thigh abduction (gluteus Medius, etc.)	Sit with your hands behind your back, keep your back straight, fix your ankles with an elastic band, straighten your legs, keep your left leg still, and stretch your right leg as far out as possible until you can't go any further, hold for 3 to 5 seconds, then slowly retract. Alternate between left and right for 1 to 2 sets. Rest for 2 to 3 minutes between sets

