Periodised progression follows dual-indicator control: volume progression (one additional set per exercise every 4 weeks, maximum 3 sets), intensity progression (resistance-band upgrade when RPE ≤ 4 with 15 standard repetitions), and density progression (inter-set rest reduced from 120 seconds to 75 seconds after week 12).

Smart components: each participant receives a Huawei Band 10 smart wristband that monitors heart rate, fall events, and blood pressure via Bluetooth synchronisation to the community health management platform. Training completion is recorded through WeChat-based manual check-in. A WeChat mini-programme delivers daily training prescriptions with illustrated guidance. The system includes automated training reminders and safety alerts (abnormal heart-rate detection triggers rest prompts and staff notification).

Personnel support: trained staff provide in-person guidance during the first week, with monthly on-site supervision thereafter. A designated team member contacts each participant weekly via WeChat to address questions and maintain adherence. Health education includes monthly group lectures and weekly one-on-one technique correction sessions.

Safety measures: pre-training medical screening (physical examination and exercise-risk assessment), individualised modifications for comorbidities (e.g., extended warm-up and blood-pressure monitoring for hypertensive patients), on-site emergency equipment (first-aid kit, AED), and a formal adverse-event reporting mechanism with monthly review and immediate reporting of serious events to the ethics committee.

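### Sub-study 2 promises a minimum effective training frequency, but all trainees share one prescribed frequency and dose is defined as volume, so it can support only an exploratory association with sessions achieved

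*Protocol*

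**What the plan says.** **Aim.** Section 1.4.2 gives Sub-study 2 the task "to analyse the minimum effective frequency of RT and to explore nonlinear relationships" between training frequency and BMD or balance, and of identifying thresholds. Section 1.4.4 presents a penalised spline with k = 3 as "stably identifying threshold effects of training frequency on BMD improvement under" sample sizes below 100. H2 in section 3.2.2 expects a J- or U-shaped curve and an optimal dose range.

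**Design.** Section 4.1.1 describes two arms "with 1:1 allocation to the intervention and control groups". Controls get health education without systematic resistance training (4.3.2). For the training arm, section 4.3.1 states "Frequency: 3 sessions/week", in both its table and its text, whereas section 1.4.1 speaks of "8 months of supervised training (twice weekly"). These statements conflict and must be reconciled. Either way, one value applies to every trainee.

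**Exposure.** In section 3.2.2, "dose is quantified as cumulative resistance-training volume", and section 3.3.1 repeats that definition. The share of planned sessions completed appears separately, under adherence. No formula for volume is given.

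**Load.** Under section 4.3.1, bands rated 4.5 to 13.6 kg are assigned from a baseline functional assessment. The progression rule is "intensity progression (resistance-band upgrade when RPE" is 4 or less with 15 standard repetitions).

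**Label.** Section 4.1.2 calls Sub-study 2 an observational dose–response analysis under STROBE.

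**The concern.** A minimum effective frequency is a statement about what would happen if people were assigned different numbers of weekly sessions. This trial assigns one number. Participants who train less often do so because they missed sessions, and the Protocol gives reasons why that is unlikely to be random: they are told to check symptoms, blood pressure and blood sugar beforehand and to stop if unwell (Table 4.3.1 (1)), and H4 in section 3.2.4 expects those without technology experience to drop out.

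The objective names one exposure (frequency) and the hypothesis another (volume). If volume counts resistance, two people with the same attendance can have different doses because one is stronger or has responded better. Dose would then partly be a result of the response it is meant to explain.

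The fitted curve is likely to be read as guidance on how many sessions a week are enough, and the observational label does not withdraw the conclusions promised in 1.4.2, 1.4.4 and 3.2.2.

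**Working it through.** The Protocol gives no power or error rate for Sub-study 2, and no sample size beyond the reference to n below 100, so there is no planned figure to reproduce. The check is whether the exposure carries the information the objective needs.

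**1. Variation in frequency.** Eight months is 8 × 365.25 / 12 / 7 = 34.8 weeks.
- At three a week: 3 × 34.8 ≈ 104 planned sessions for everyone. At two a week: about 70 for everyone.
- Prescribed frequency therefore has zero variance among trainees. Controls add only a point at zero, which cannot locate a minimum between zero and the prescription.
- Section 1.3.4 targets adherence above 70%. If individuals lie between 70% and 100% (my assumption), achieved frequency runs from 0.7 × 3 = 2.1 to 3.0 a week, a span of 1/0.7 = 1.43-fold (1.4 to 2.0 if two are prescribed).

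**2. Volume against frequency, if volume includes load.** The band ratings span 13.6 / 4.5 = 3.02-fold. Assume volume = load × sessions, the four bands used equally, and attendance uniform and independent of load. Then log volume = log load + log attendance, which gives:

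| Attendance range | Share of log-volume variance due to load | Correlation of volume with achieved frequency |
|---|---|---|
| 70–100% | 94% | 0.25 |
| 50–100% | 81% | 0.43 |
| 30–100% | 59% | 0.60 |
| 10–100% | 32% | 0.73 |

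**3. False dose signal through load.** The simulation had no true frequency effect, band set by strength, and strength correlated r with BMD change. It used an unadjusted linear test at two-sided 5%, with 4,000 runs per setting.
- r = 0.3, attendance 70–100%: the volume–outcome test was significant in 47% of runs (n = 50) and 73% (n = 90).
- r = 0.3, attendance 30–100%: 32% and 52%.
- r = 0: about 5%.
- With attendance itself as the exposure, the rate stayed near 5% in all these settings, because attendance was generated independently of strength.

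**4. False dose signal through attendance.** Let a health factor correlate r with both attendance and BMD change. The mean of a standard normal variable in its top quarter is 1.271, so the spurious gap between top and bottom attendance quarters is 2 × 1.271 × r² × SD of change.
- r = 0.3, SD 2.5%: 2 × 1.271 × 0.09 × 2.5 = 0.57 percentage points.
- r = 0.4, SD 3.5%: 2 × 1.271 × 0.16 × 3.5 = 1.42.
- r = 0.5, SD 3.5%: 2 × 1.271 × 0.25 × 3.5 = 2.22.

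Section 1.4.1 expects a lumbar gain of at least 3%. In simulation with r = 0.4 for both links, an unadjusted attendance–outcome test was falsely significant in 18% (n = 45) and 31% (n = 90) of runs.

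The correlations and SDs in steps 3 and 4 are mine; the Protocol gives none. Both steps are before any covariate adjustment.

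**The case against.** Several stronger readings are tempting, and the Protocol does not support them.

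- **That the sub-study can answer nothing.** Half of the objective is to explore nonlinear relationships, completed sessions are recorded, and section 4.1.2 already labels the analysis observational. An exploratory association with achieved sessions remains available.
- **That dose is a load measure set by the participant's strength.** No passage says volume includes band load. Section 3.2.2 places intensity attainment under adherence, apart from dose, so volume could mean sessions, sets or repetitions. Steps 2 and 3 apply only if load counts. Even then, 3.02-fold compares the lightest band throughout with the heaviest throughout, and load's share falls to 32% when attendance is very wide.
- **That the upper part of the curve cannot be seen.** H2 allows benefit to plateau as well as decline. A plateau below full prescription could show without anyone exceeding it, and nothing in the text establishes how many would exceed it.
- **That bias must favour high attenders.** H1 in section 3.2.1 expects a larger response in people with lower baseline BMD, so confounding could run the other way.
- **That confounding is left unadjusted.** Sections 3.3.1 and 3.3.3 list T-score, comorbidity, medication, nutrition and baseline activity among the covariates. These would reduce the gap in step 4 by an unknown amount.

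All of this limits the size and form of the concern. None of it removes the core: adjustment cannot create variation in assigned frequency, a k = 3 spline restrains overfitting but not confounding, and volume on any definition is not the frequency named in the objective.

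**Conclusion.** The concern holds in a limited form. With one prescribed frequency for all trainees, the trial can describe how outcome relates to sessions achieved. It cannot establish a minimum effective frequency, a frequency threshold or an optimal dose. This follows from the design and the stated definitions and rests on no numerical assumption. The mismatch between frequency in 1.4.2 and 1.4.4 and volume in 3.2.2 and 3.3.1 is likewise plain from the text.

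The size is less certain. The 3.02-fold load span matters only if volume includes load, and the 0.6 to 2.2 point gap rests on assumed correlations and SDs without adjustment. Both show that the distortion could be material against an expected 3% gain; neither predicts it. The randomised primary comparison is not affected. The change should be made before the sub-study is analysed.

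**What to change.** In sections 1.4.2, 1.4.4 and 3.2.2, with matching wording in 3.3.1:

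1. Make sessions completed per week the exposure for Sub-study 2. Keep cumulative volume as descriptive, with a stated formula that says whether band load counts.
2. Add baseline grip strength, SPPB and starting band to the covariates in 3.3.1 and 3.3.3, and use baseline lumbar BMD as a continuous value.
3. Describe the result as an exploratory association. Remove the minimum effective frequency, the stable identification of thresholds and the optimal dose range as conclusions.
4. State that the curve is not interpreted beyond the observed attendance range.
5. Reconcile the prescribed frequency between 1.4.1 and 4.3.1, since the planned number of sessions is the denominator for adherence.

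The cost is mainly rewording. Completed sessions, grip strength, SPPB and BMD are already scheduled; the starting band is already assigned and needs only to be recorded. The price is a weaker claim for the sub-study. Keeping the stronger claim would require randomising frequency, which is a different trial.
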